We will recruit 280 participants; 70 in each of the four arms. Wiberg-Itzel et al [2] observed mean umbilical artery pH 7.23 (SD 0.07) in the non-intervention group. With our sample size, we will have 80% power (significance level 0.05) to detect mean pH changes of 0.04 and above in each arm. We are interested in detecting an effect size of 0.2 and above, which we deem to be a moderate effect size. The total sample size needed to detect a between-factor mean effect size of 0.2, by repeated measures analysis of variance (ANOVA) with a type 1 error margin of 5%, across 4 groups with 5 repeated measurements; was 224 at a power of 91%. Assuming a 20% loss to follow up in our study; we will need 280 participants (70 in each of the 4 groups). The sample size was calculated using G* Power software version 3.1 using the test family for the F test, and the statistical test for ANOVA repeated measures, between factor analysis & within-between interaction [10]. Therefore, our sample size will also be sufficient to detect a within and between-subject interaction (intervention and time interaction) with a power of 99%. To obtain these estimates, we will construct an interaction term between the intervention and the time variable. We are confident that we shall be able to accrue this number of participants in a period of six calendar months, on the basis of our experience working in the same hospital [7]. In order to detect a change in maternal pH, a minimum of two measurements are needed from a participant. However, with improvement of obstetric care, many women deliver within 30 minutes of taking the baseline measurements and hence no second measurement is obtained. To account for this form of right censoring, we have inflated our sample size by 192 participants to ensure that we have at least 280 women with at least two pH measurements. We will recruit 472 participants; 118 in each of the four arms.

Outcome variables

The primary outcome measure will be the mean change in maternal pH from baseline in each group. The secondary outcomes will include, mean pH and lactate in maternal and umbilical blood, early neonatal death, safety (side effects) of sodium bicarbonate, primary PPH, sepsis and death. Furthermore, the plasma concentrations of HCO₃ levels will be measured as well to accurately estimate the required dose.

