Data analysis plan

Data will be analyzed using Stata version 17.0 (StataCorp; College Station, TX, USA). We will describe categorical variables as proportions and compare them with chi-squared tests or Fischer's exact tests as appropriate. We will describe continuous variables as means (SD) OR medians (IQR) and compare them with t tests or Mann-Whitney U tests as appropriate. Our analysis will be by intention to treat. To determine the safety of sodium bicarbonate infusion, we will compare the incidence of side effects in each arm and report risk differences.

For the primary outcome of acidosis (pH and lactate) between-subjects repeated measures ANOVA will be conducted. We will also conduct within-subject interaction repeated measures ANOVA to assess for differences in the rate of change of pH between the groups.

We will use histograms, P-P plots, k-density, and Q-Q to assess the distribution of normality of continuous outcomes. In case the distribution of normality is not met; we shall transform our data and this decision will be guided by Stata's *gladder* command that shows various transformation options.

All analyses will be followed by a Bonferroni posthoc test for multiple comparisons, a Friedman test to compare rates of change between the various groups, and a Mauchly's test of Sphericity to check for equal variance among the combinations of the various groups. We will use Margins and Margins plots to obtain marginal means and graphical descriptions of the interaction between various groups and time.

Data Monitoring

Independent Data Monitoring Committee (IDMC)

An independent data monitoring committee (IDMC) will be appointed consisting of 3 members: a statistician, an obstetrician/gynaecologist, and a paediatrician. They will operate according to the IDMC charter, which will be developed with the members. IDMC will be encouraged to follow the recommendations of the international DAMOCLES group for IDMC activities.[12] The IDMC will monitor the trial once with a focus on issues relating to the quality of trial conduct, such as overall and site-specific rates of recruitment, adherence to trial interventions, visit schedules, losses to follow-up, and administrative and safety data. It will review administrative and safety data approximately every three months. The treatment groups will be masked in the IDMC reports.

Interim analyses and stopping guidelines

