Interim analyses: The interim analysis of efficacy data will be performed by the IDMC statistician. One analysis will be conducted according to the group sequential design when 50% of the inclusions are recorded. According to the O'Brien-Fleming alpha spending function, using a group sequential design and assuming a power of 80% and a significance level of 5%, the first interim analysis includes 140 subjects and has an information rate of 50%, efficacy bounds of -2.96 and 2.96, and p-value 0.003 (figure 3). These calculations were made using the RPACT RShiny app (<https://rpact.shinyapps.io/public/>). Interim trial data will be kept confidential and restricted to the IDMC, except if early stopping of the trial is recommended.

[figure not shown]

Figure 3: Figure showing efficacy bounds (critical value) at the interim analyses (50% accrual rate) and how these will change as the study progresses

Stopping guidelines

1. We propose the following stopping rule: “a statistically significant difference ($p \leq 0.003$) at the interim analysis according to the O'Brien-Fleming spending function for group sequential design) in the primary outcome between the treatment arms.
2. SAEs will be continuously monitored during data entry and reported to the IDMC. Any imbalance between expected occurrence and actual occurrence will be assessed by the IDMC statistician when 50% inclusions are recorded, and discussed with the IDMC.
3. The IDMC will provide a recommendation to stop or alter the design or conduct of the trial in case of high efficacy and/or poor adherence or unacceptable side effects that can be ascribed to the intervention according to pre-determined stopping rules and criteria. While the reviews of safety will consider both expected or unexpected adverse events, and the relative rates of death.
4. If the IDMC recommends stopping the trial early, a meeting of the principal investigator, the trial sponsor, the trial steering committee and the IDMC will be held to decide on the trial discontinuation. In case of disagreement, the advice of independent external experts will be sought. A report will be submitted to the Local IRB (BUIRB) as soon as possible and not later than 14 days after the decision.

Ethics and consent process

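### Two omnibus tests serve the primary pH outcome and the plan does not say which decides; if either may count, the false-positive rate is up to about 10%, not 5%

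*Combined protocol and SAP*

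**What the plan says.** The Data analysis plan gives the primary outcome a between-arm test: "For the primary outcome of acidosis (pH and lactate) between-subjects repeated measures ANOVA will be conducted". The next sentence adds an arm-by-time test on pH: "We will also conduct within-subject interaction repeated measures ANOVA to assess for differences in the rate of change of pH between the groups". A Bonferroni step follows every analysis as a post hoc procedure. Mauchly's test is listed, but no action is attached to its result.

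Sample size estimation and sampling sizes the trial "by repeated measures analysis of variance (ANOVA) with a type 1 error margin of 5%, across 4 groups with 5 repeated measurements"; the total for the between-factor effect "was 224 at a power of 91" per cent. It then says that "our sample size will also be sufficient to detect a within and between-subject interaction (intervention and time interaction) with a power of 99" per cent.

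Outcome variables defines the primary outcome as the change in the mother's pH from its baseline value.

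Under Stopping guidelines, the trial may stop at p ≤ 0.003 for a difference "in the primary outcome between the treatment arms". The rule does not say which test supplies that p-value.

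**The concern.** The two tests ask different questions. The between-arm F test compares average level over the repeated measurements. The arm-by-time F test compares the shape of the profiles. Arms that differ by the same amount at every analysed time move the first and not the second; arms that separate gradually from a common start can do the reverse.

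No section ranks the tests or splits alpha. The Bonferroni step handles comparisons among arms within an analysis, not the choice between analyses. A reader who tries to infer the deciding test gets mixed signals: the sizing text favours the between-arm test, while the outcome definition is a change from baseline, which averaging raw pH with baseline included does not measure.

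At stake are the error rate behind any efficacy claim, the p-value the IDMC statistician should hold against 0.003, and which power figure (91% or 99%) belongs to the trial. The problem exists for pH alone, apart from the question of whether lactate is also primary.

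**Working it through.** **Inputs.** From Sample size estimation and sampling: effect size f = 0.2, k = 4 groups, m = 5 measurements, alpha 5%, N = 224, 20% loss. From Interim analyses: 50% information, bound ±2.96, p = 0.003. The documents do not give the correlation ρ between repeated measurements; 0.5 is assumed because it reproduces the stated figures.

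**The plan's own figures.**
- Between factor: λ = N f² m / (1 + (m − 1)ρ) = 224 × 0.04 × 5 / 3 = 14.93, on 3 and 220 df. Power is 91.06%; stated 91%.
- Interaction: λ = N f² m / (1 − ρ) = 224 × 0.04 × 5 / 0.5 = 89.6, on 12 and 880 df. Power is above 99.9%; stated 99%.
- Loss: 224 / 0.8 = 280, as stated.
- O'Brien-Fleming spending at 50% information: bound 2.963, two-sided p = 0.00305, as stated. The matching final level is 0.0490.

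**Two routes to success.** If the tests were independent and each used 5%, the chance of at least one false positive would be 1 − 0.95² = 9.75%; the upper bound by summing is 10%.

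**Null simulation.** Four arms of 56, complete data, five times, 30,000 replicates per covariance. GG is the Greenhouse-Geisser correction of the interaction F.

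| Covariance (assumed) | Between | Interaction, uncorrected | Either, uncorrected | Either, GG |
|---|---|---|---|---|
| Compound symmetry 0.5 | 4.8% | 4.9% | 9.5% | 9.4% |
| AR(1) 0.5 | 4.8% | 6.4% | 10.9% | 9.6% |
| AR(1) 0.7 | 5.0% | 7.6% | 12.2% | 9.6% |
| AR(1) 0.8 | 5.0% | 8.3% | 12.8% | 9.8% |

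With 70 per arm and AR(1) 0.85 (8,000 replicates), the uncorrected either-test rate is 13.5%. So the doubling to about 10% comes from having two tests. The excess over 10% comes from non-sphericity with an uncorrected F.

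**Interim look.** Allowing both tests at p ≤ 0.003 at half the sample, with the final level left at 5%, gives 9.7% under compound symmetry. The interim look hardly changes the size of the problem.

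**Which test finds an effect depends on its shape.** Assumptions: 56 per arm, SD 0.07, effect graded across doses up to 0.04 at the top dose, interaction GG-corrected where baseline is included.
- Post-dose values only, prompt constant shift, compound symmetry 0.5: between 94%, interaction about 5%.
- Baseline included, prompt constant shift, compound symmetry 0.5 or AR(1) 0.7: between 83–85%, interaction 55–73%. Stronger serial correlation can reverse this order.
- Baseline included, linear divergence, the same two covariances: between 38–39%, interaction 45–64%. Across these and AR(1) 0.85, the two tests gave different verdicts in 49–57% of simulated trials.

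**Splitting alpha.** Both tests at 2.5%, with GG on the interaction, give 4.6–5.2% overall. Between-test power at N = 224 and ρ = 0.5 falls from 91% to 85.6%; regaining 91% needs about 260 evaluable women.

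**The case against.** The best counter-argument is that the between-arm test is already primary by implication. It is the test attached to the primary outcome, N = 224 is derived from it, the interaction is introduced each time as an addition, and the stopping rule speaks of a difference between arms. On that reading the error rate is 5%. This stands as a plausible reading, and so a flat statement that the trial runs at 10% or more is not supported. It remains an inference: no section states it, and it sits badly with an outcome defined as change from baseline unless the analysed values are change scores or baseline-adjusted, which the plan does not say.

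Three further points stand. The Data analysis plan states no alpha, so 5% for each test is inferred from the sizing text. The quoted 99% cannot confirm it, since interaction power exceeds 99.9% at alpha 0.05 and also at 0.001. The simulations use complete, balanced data, while the protocol expects many women to deliver before a second sample, so the rates are indicative. And the IDMC charter, which might name the interim test, is not part of the document.

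A reader might also infer that the arm-by-time test should decide because the outcome is a change. The documents do not support that. If the five measurements are the post-dose samples from 30 to 150 minutes in Table 1, the interaction has almost no power for a prompt, sustained shift.

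The description of the study as a dose-ranging pilot does not remove the point, because the plan includes a formal efficacy stop.

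**Conclusion.** The point holds as a gap in the decision rule. Two omnibus tests apply to primary pH, nothing says which decides, and alpha is not divided.

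Its size is conditional:
- 5% if the between-arm test alone decides.
- Up to about 10% if either may declare success, taking 5% for each.
- About 11–14% if, in addition, sphericity fails (assumed AR(1) 0.5–0.85) and the interaction F is uncorrected.

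The last range should not be read as the cost of multiplicity: with a Greenhouse-Geisser correction the rate returns to 9.4–9.8%. Nor is it established for this trial, because the documents give no covariance. It is possible under the plan as written, since Mauchly's test has no stated consequence.

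This should be settled before the interim analysis, because the p ≤ 0.003 rule cannot be applied unambiguously without it.

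**What to change.** In the Data analysis plan, name one deciding test for maternal pH that tests change from baseline. One suitable choice is the between-arm comparison of post-dose pH adjusted for baseline (or of change scores) in a repeated-measures model with unstructured covariance. Make the arm-by-time test supportive, with a Greenhouse-Geisser correction if ANOVA is kept.

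Alternatively, keep both tests at 2.5% each, with that correction on the interaction.

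Under Stopping guidelines, state that the interim p ≤ 0.003 comes from the deciding test. Under Sample size estimation and sampling, give that test's power as the trial's power, with the assumed correlation and whether baseline is one of the five measurements.

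**Cost.** With one deciding test, the change is wording plus a restated power calculation, and a trial positive only on the supportive test could not claim success. With split alpha, between-test power falls from 91% to about 86% at N = 224 (assumed correlation 0.5), or about 260 evaluable women are needed to hold 91%.

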neonatal deaths despite being resuscitated. A potential way of improving maternal and perinatal outcomes among women with OL would be to buffer the excess lactic acid with sodium bicarbonate, achieving intrauterine resuscitation whilst awaiting an emergency cesarean section. However, in this situation, there is inadequate time (or staff) to correct the acidosis through careful titration of the bicarbonate infusion. A universal safe and effective dose would therefore facilitate its use. In our previous RCT, a single dose of 4.2g was insufficient to achieve changes in maternal or neonatal lactate levels. It is not known if a higher dose of bicarbonate would reverse the acidosis and achieve clinical benefits for the mother and baby. Therefore, we propose to undertake a placebo-controlled, dose-ranging pilot trial to determine the efficacy and safety of a preoperative infusion of sodium bicarbonate on acidosis, compared with placebo among women with obstructed labour (OL).

Justification

Undertaking a placebo-controlled, dose-ranging pilot trial shall establish a universal safe and effective dose of sodium bicarbonate for use to correct the acidosis among women with obstructed labour. Our results will inform the design of a full-scale effectiveness phase III trial to determine the effect of this preoperative infusion on maternal and perinatal outcomes. Furthermore, this information will facilitate the inclusion of sodium bicarbonate infusion in the standard preoperative preparation for women with obstructed labour in a low resource setting.

Objectives

General objective

To determine the efficacy and safety of a preoperative infusion of sodium bicarbonate on pH and lactate levels (metabolic acidosis) among women with obstructed labour.

Specific objectives

1. To determine the efficacy of a preoperative infusion of sodium bicarbonate on acidosis, compared with placebo among women with obstructed labour (OL).
2. To determine the safety of a preoperative infusion of sodium bicarbonate compared with placebo among women with obstructed labour (OL).

Hypothesis

We hypothesize that a higher dose of bicarbonate can safely lower the lactate levels (metabolic acidosis) by at least 20%.

Methods and materials

Study design

We will conduct a dose-finding phase III, randomized, double-blind, placebo-controlled, parallel-group trial.

Study setting

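### The scale of the primary analysis is left to a transformation chosen from plots of the trial data, although the outcome is defined and powered in pH units

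*Combined protocol and SAP*

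**What the plan says.** Under Outcome variables: "The primary outcome measure will be the mean change in maternal pH from baseline in each group". The sample size section plans this in pH units: a change of 0.04, with an SD of 0.07 taken from umbilical artery pH in a cited study. The Data analysis plan widens the primary outcome to include lactate: "For the primary outcome of acidosis (pH and lactate) between-subjects repeated measures ANOVA will be conducted".

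The same section then sets the rule at issue. First comes a visual check: "We will use histograms, P-P plots, k-density, and Q-Q to assess the distribution of normality of continuous outcomes". Then the action: "In case the distribution of normality is not met; we shall transform our data". The choice of transformation is left to a display of the data: "this decision will be guided by Stata's *gladder* command that shows various transformation options". Results are to be presented as marginal means ("We will use Margins and Margins plots to obtain marginal means"), with no scale stated.

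The plan gives no threshold for calling a distribution non-normal, no named transformation and no back-transformation. It does not say whether pH levels, pH changes or model residuals are examined, or that the choice is made blind to arm. The section on interim analyses tests the same primary outcome for efficacy at p ≤ 0.003, and nothing requires the interim and final analyses to use the same scale.

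**The concern.** A primary effect should be stated on a scale fixed before the data are seen. Here the scale can change once the plots have been inspected. A difference in, say, squared or reciprocal pH cannot be set against the 0.04 pH units on which the trial was planned, and with no back-transformation rule the main result may not be readable in pH units at all. Because the check is visual, two analysts could reach different scales from the same data, and the interim and final looks could differ.

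The tool also fits the outcome poorly. A power ladder is built for positive variables with a wide relative range. A pH change is signed, and raw pH is positive but varies over a very narrow relative range. The question is whether the rule could do any good for either, and whether the analysis needs it.

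**Working it through.** **1. The plan's own figures.** Inputs from the sample size section: f = 0.2, 4 groups, m = 5 measurements, N = 224, alpha 0.05. The plan states no correlation between measurements; assume ρ = 0.5. Then λ = f²·N·m / (1 + (m−1)ρ) = 0.04 × 224 × 5 / 3 = 14.93 on (3, 220) df. Power is 91.1%, matching the stated 91%. (It would be 97.5% at ρ = 0.3 and 82.6% at ρ = 0.7.) With 20% loss, 224 / 0.8 = 280, as stated.

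The pH sentence is conservative. For a two-arm comparison, n = 2 × 0.07² × (1.96 + 0.84)² / 0.04² gives 49 per arm for 80% power. Power is 92% at 70 per arm and 86% at 56. These planning figures stand as long as the effect stays in pH units.

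**2. If the ladder is applied to change scores.** The SD of maternal pH change is not in the documents. Taking 0.07 as the SD of a single pH value, SD of change = 0.07 × √(2(1−ρ)), with ρ assumed between 0.3 and 0.9. Under a normal model, P(change < 0) = Φ(−mean/SD):

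| ρ | SD of change | mean +0.02 | mean +0.04 |
|---|---|---|---|
| 0.3 | 0.083 | 40% | 31% |
| 0.5 | 0.070 | 39% | 28% |
| 0.7 | 0.054 | 36% | 23% |
| 0.9 | 0.031 | 26% | 10% |

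(The first entry in the last column is 31.5% before rounding.) With a mean change of 0 the share is 50% whatever the SD. Log and square root do not exist for these values. The square exists but removes the sign: with SD 0.07, true means of −0.02 and +0.02 give the same mean square.

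**3. If the ladder is applied to raw pH.** For simulated pH with mean 7.23 and SD 0.07, every step from the cube to the inverse cube has an absolute correlation of at least 0.999 with pH itself. For a left-skewed version with skewness −2.0, skewness becomes −1.89 (cube), −1.94 (square), −2.03 (square root) and −2.06 (log). The reciprocals reverse the order and leave skewness of 2.1 to 2.3. No step repairs the shape.

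**4. Is the rule needed to protect the test?** Four-arm null trials with 56 per arm (224 / 4) were simulated and analysed by an untransformed one-way F test at 5%. Type I error was about 4.9% for exponential data, 4.2% for lognormal and 4.6% for t with 3 df; repeat runs differ by a few tenths of a point. At 35 per arm (the 140-subject interim divided by 4) it was about 4% to 5%. These runs used the 5% level and independent values, not the interim threshold or the repeated measures model.

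**5. Lactate.** Lactate levels are positive and probably skewed, so here a transformation can help. Assume lognormal lactate, a 20% fall, 56 per arm and a two-arm t test. Power is 59% raw against 64% logged at log-SD 0.5, and 19% against 25% at log-SD 0.9. The gain is modest, and it is available without any search if the log is named in advance.

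**The case against.** The strongest reply is that the planned model is a repeated measures ANOVA with a treatment-by-time interaction, and Table 1 schedules pH at baseline and every 30 minutes to 150. The natural dependent variable is then pH at each time, which is always positive, so every ladder step is defined. This stands as a possible reading. A reader might infer from the signed outcome that women whose pH falls will be dropped, or the direction of effect lost. The documents do not support that. They do not say that change scores are transformed, that an undefined step would be chosen, or that negative values would be discarded; the display only guides the choice. The shares in the table also come from a normal model, under which the rule would not be triggered, so they illustrate how common negative changes are and do not forecast exclusions.

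A reader might also infer an inflated false-positive rate. For raw pH, even taking the smallest p-value over the whole ladder gives only 5.2%. For lactate the same worst case gives about 12% (assumed lognormal, median 6.9, log-SD 0.9), but the plan chooses by distribution shape and nowhere by significance.

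Finally, the hypothesis that bicarbonate "can safely lower the lactate levels (metabolic acidosis) by at least 20"% might be taken to fix the log scale. It does not: 20% could equally refer to the baseline mean or the placebo mean.

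None of this supplies a fixed scale. On the raw pH reading the rule is harmless to the test but does nothing useful.

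**Conclusion.** The point holds as one of pre-specification and interpretability. On the change-score reading the ladder is unsuitable, because several of its steps are undefined or lose direction. On the raw pH reading it is ineffective. Either way, if the plots are judged non-normal, the primary effect moves off the 0.04 pH-unit scale to one chosen after seeing the data.

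The size is small. The switch is conditional on the plots, no bias in the planned test has been shown, and the sample size is unaffected. The 10% to 32% of negative changes at a mean of +0.04 rests on an assumed SD of change of 0.031 to 0.083 and a normal model. The statement that transformation is not needed to protect the test rests on a one-way F test, and its extension to the repeated measures model is a reasonable expectation that was not checked.

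**What to change.** In the Data analysis plan, replace the ladder rule for the primary outcome with a scale fixed in advance and used at both the interim and the final analysis:

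- pH: analyse untransformed and report differences in pH units, with model-based or robust standard errors.
- Lactate: analyse on the natural log scale and report ratios of geometric means. State that a 20% fall is read as a ratio of 0.80, which is one reasonable reading of the hypothesis that the plan would now be adopting.
- Plots: use them to check model residuals only. Any rank-based or otherwise transformed analysis is a sensitivity analysis.

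The cost is a few sentences, with no change to sample size, data collection or conduct. The one downside is that the lactate result is reported as a ratio rather than in mmol/L; descriptive means or medians in mmol/L by arm can stand beside it.

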Randomisation: A sequence of random numbers will be generated by an independent biostatistician using an online randomization service at www.sealedenvelope.com in permuted block sizes of four, six and eight. An independent, off-site pharmacist will prepare and consecutively number identical study packages using

the generated random numbers. This will ensure that the allocation is concealed. At the study site, after gaining consent, the research midwife will take the next sequentially labeled study drug package and administer its contents to the eligible participant. Therefore, both the participants and data collectors will remain blinded throughout the study.

Intervention/ Comparator: Eligible participants will be randomly assigned to receive 100 mls (8.4g), 150 mls (12.6g) and 200 mls (16.8g) of 8.4% sodium bicarbonate solution, or placebo (50 mls of NS 0.9%) in a ratio of 1:1:1:1. The study drug (Sodium Bicarbonate 8.4% and Normal Saline 0.9%) will be contained in identical 25 mL glass vials (Neon Laboratories Ltd, Mumbai, India), administered intravenously as a single bolus dose. Since the average waiting time for CS in our labour ward is approximately 110 minutes [11], there will be no need for a repeat dose.

In addition, all patients will receive the available Ministry of Health recommended standard preoperative care for all patients with OL which includes antibiotic prophylaxis, intravenous fluid replacement (1.5 L of normal saline), bladder drainage and lying in left-lateral position as they are being prepared for caesarean section [23]. Details in flow diagram 1.

Data collection

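### The Friedman test named for comparing rates of change between arms cannot make that comparison: it tests for a time trend within women, so its p-value would be mislabelled

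*Combined protocol and SAP*

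**What the plan says.** The trial is a "dose-finding phase III, randomized, double-blind, placebo-controlled, parallel-group trial" (Study design), with women allocated equally to three bicarbonate doses or placebo. Table 1 schedules pH at baseline and at 30, 60, 90, 120 and 150 minutes, and again at birth.

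The Data analysis plan names two procedures for the same question:

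- a "within-subject interaction repeated measures ANOVA to assess for differences in the rate of change of pH between the groups";
- after all analyses, "a Friedman test to compare rates of change between the various groups".

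Nothing else in the document redefines the Friedman test, applies it to slopes, confines it to description within an arm, or says which of the two results governs if they disagree.

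**The concern.** The Friedman test compares related conditions within matched blocks. The four arms here are different women, so the only matched values are one woman's own repeated samples. Used in the ordinary way, the test therefore asks whether pH changes over time, not whether it changes at a different rate in different arms.

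A trend common to all arms is plausible. Under Intervention/Comparator every woman receives 1.5 L of normal saline and the same standard preoperative care, and labour continues meanwhile. Such a trend would yield a small p-value that the plan labels as a difference between groups. In a dose-finding trial meant to inform a full-scale trial, that p-value could be read as a dose effect. A large p-value could equally seem to contradict a true arm-by-time effect.

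**Working it through.** **1. The plan's own figure.** No power or size is stated for the Friedman test. The sample size rests on repeated measures ANOVA: total N = 224, effect size f = 0.2, four groups, m = 5 measurements, alpha 5%, stated power 91%. The within-woman correlation ρ is not stated; 0.5 is assumed.

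- λ = N f² m / (1 + (m − 1)ρ) = 224 × 0.04 × 5 / (1 + 4 × 0.5) = 44.8 / 3 = 14.93. With 3 and 220 df the power is 91.06%, which agrees.
- 224 / (1 − 0.20) = 280, which agrees.

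The sample size therefore does not rest on the Friedman test.

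**2. What the statistic contains.** With b women as blocks and k times as conditions,

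χ² = 12 / [b k (k + 1)] × Σ Rⱼ² − 3 b (k + 1), on k − 1 df,

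where Rⱼ is the sum over women of the within-woman rank at time j. For 280 women and six times, b = 280, k = 6 and df = 5. The arm label appears nowhere, and the null hypothesis is that there is no time trend. This follows from the definition and needs no assumed figure.

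**3. Illustration by simulation.** Assumed, not in the documents: between-woman SD 0.05 and within-woman SD 0.05, linear drift over 0–150 minutes, complete series, 70 women per arm, six times, nominal alpha 5%. The total SD is √(0.05² + 0.05²) = 0.07. That matches the SD in the sample size section, which is for umbilical artery pH, not maternal pH. Repeated runs of 1,500 to 2,000 trials per scenario agree closely.

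| Scenario | Friedman, all women pooled | Arm-by-time F test |
|---|---|---|
| Identical arms, no drift | 4–5% | about 5% |
| Identical arms, shared drift 0.01 | about 45% | about 5% |
| Identical arms, shared drift 0.02 | about 99% | about 5% |
| Identical arms, shared drift 0.04 | 100% | about 5% |
| Arm drifts −0.03, −0.01, +0.01, +0.03 | about 5% | about 99% |

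**4. Sensitivity.** A second set-up used 56 women per arm (224 / 4), five times and SD 0.07.

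- ρ = 0.5, identical arms, shared change 0.02: Friedman 94.6%, interaction 5.0%.
- ρ = 0.8, same scenario: Friedman 100%, interaction 4.1%.
- Arm changes of −0.04, −0.013, +0.013 and +0.04: Friedman 4.1% (ρ = 0.5) and 2.9% (ρ = 0.8); interaction 100% for both.

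**5. Other ways to run the test.**

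- *Separately in each arm.* This gives four tests of trend and no between-arm test. If each identical arm is significant with probability p, some but not all are significant with probability 1 − p⁴ − (1 − p)⁴. In the first set-up this happened in about 18%, 44%, 86%, 50% and 6% of trials at shared drifts of 0, 0.01, 0.02, 0.03 and 0.04.
- *Times as blocks, arm means as conditions.* The blocks contain the same women, so they are not independent. With identical arms this rejects in about 60% of trials in the first set-up, and in 49% (ρ = 0.5) to 86% (ρ = 0.8) in the second. It also responds to level rather than rate: constant arm shifts of 0, 0.02, 0.03 and 0.04 with no change over time give 99.5% rejection (ρ = 0.5).

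**The case against.** The strongest reply is that the question is already answered. The paragraph before the Friedman sentence plans an interaction analysis aimed at differences in rate of change, and margins plots of group by time follow. The interim stopping rule refers to the primary outcome and does not mention Friedman. This stands, and it sets the limit on the harm. What it leaves open is that the plan names two tests for one question, gives neither precedence, and one of them does not address it.

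Several stronger readings are tempting but not supported:

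- *That the test will be significant whenever the arms are identical.* This needs a trend shared by the arms. With none, it rejects at about the nominal 5%, and the documents give no size for a trend.
- *That it generally misses real differences.* The 5% figure needs arm trends that cancel. In the first set-up, drifts of 0, 0.02, 0.03 and 0.04 give over 99% rejection, and −0.01, 0.01, 0.02 and 0.03 give about 67%. Those rejections still do not compare arms, but they are not misses.
- *That by-arm results would nearly always conflict.* The 86% at drift 0.02 lies close to the mathematical ceiling of 1 − 2 × 0.5⁴ = 87.5%, and the figure falls to about 6% at drift 0.04. Nor does the plan say that by-arm p-values would be compared.
- *That missing late samples single out this test.* The plan says "Since the average waiting time for CS in our labour ward is approximately 110 minutes", and the sample size section expects many women to deliver within 30 minutes of baseline, so complete rows will be scarce. Classical repeated measures ANOVA has the same difficulty, and both tests were simulated on complete data.

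**Conclusion.** The point holds as an error in the written plan: the Friedman test has no term for independent arms and cannot compare their rates of change. That conclusion rests only on the definition of the test and the parallel-group design.

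The size of the distortion is illustrative. Under the assumed variances, a shared pH drift of 0.02, half the 0.04 change named in the sample size section, is enough for near-certain rejection with identical arms. The variance split, the correlation, the drift sizes, the complete series and the use of an umbilical artery SD for maternal pH are all assumptions.

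A reader might infer that the primary comparison, the sample size or the interim boundary is compromised. The documents do not support that. The consequence is a mislabelled secondary p-value, worth correcting because it could be reported as evidence about dose.

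**What to change.** In the Data analysis plan, delete the Friedman test as a comparison of groups, or restrict it to describing the time trend within an arm. State that the between-arm comparison of rates of change comes from the arm-by-time interaction already planned.

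If a rank-based back-up is wanted, compute one change or slope per woman and compare the four arms by a Kruskal-Wallis test. In the second set-up (ρ = 0.5) this held its size (3.8% and 5.1% with shared changes of 0.02 and 0.04). Its caveat should be written in: women will have different lengths of follow-up, and the Introduction says that the effect in the previous trial was noticeable only after more than one hour, so short and long series do not carry the same information.

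The cost is one sentence of the plan. No new data, staff or participants are needed.
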